Our primary outcome is radiographic evidence of fracture healing at the 12-week endpoint. At 4, 8 and 12 weeks after initiating TPTD or TPTD placebo, all patients will get follow-up pelvic radiographs, although these radiographs will stop when healing occurs. If the radiologist notes cortical bridging on the monthly x-ray, or at 3 months a confirmatory limited low dose Focus CT at the fracture site(s) will be performed to assess the degree of bridging. Cortical bridging will be quantified with bridging of 3 or 4 cortices as "healing", 1 or 2 cortices as "partial healing", and 0 cortices as "minimal/no healing" by two independent radiologists and adjudication by a third. If there are multifocal fractures, cortical bridging at each site will be evaluated and an adjudicated score representing the state of healing (0 to 4) will be recorded. Secondary analysis will examine treatment group differences in the change in follow-up pelvic fracture healing scores over the repeated monthly assessments during the 3 month placebo-controlled phase.

A secondary outcome is pain and narcotic use. The numeric rating scale (NRS) will be administered by research staff that is blinded to treatment group. We will also quantify use of narcotics and other adjunct medications for pain by recording their reported use and also asking for narcotic bottles to be brought in at each visit and performing a pill count. The NRS and recording of pain medications will be done at baseline, 4, 8 and 12 week visits and at the 6, 9 and 12 month visits.

Another secondary outcome is lower extremity physical function at 3 months and again from 3-12 months. Physical performance tests will be administered by research staff that is blinded to treatment group. The lower extremity physical function tests, tests include normal walking speed over 4 meters (with or without an assistive device), repeated chair stands (stand up from a chair with their arms folded across their chest), and balance (ability to maintain balance for 10 seconds in each of 3 positions: side-by-side, semi-tandem, and tandem foot positions). In addition, the Timed Up and Go test will be completed by each subject. Each subject will also complete the survey of ADLs and the SF-36.

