#### **Protocol:**

#### **Recruitment:**

Subjects will be recruited, during their initial hospitalization (median length of stay is 9 days) or from the emergency room or physician office from Hospital for Special Surgery/New York Hospital, Lenox Hill Hospital, New York Presbyterian Queens, or Helen Hayes Hospital. The goal will be to start treatment within one month

of fracture. Since not all pelvic fractures are hospitalized, radiologists at each institution have agreed to contact us regarding patients with pelvic fractures who are not admitted. We will recruit approximately 100 subjects (female and male)  $\geq$  65 years of age over a total of 4 years (30 in years 1, 2 and 3 and 10 in year 4) to complete 80 subjects with 3 months of treatment, to accommodate a drop-out rate of 20% in the 3 month treatment portion of the study.

**Screening and Baseline visit:** Subjects will have their screening and baseline visit during their initial hospitalization or by coming into one of the participating hospitals for a follow-up orthopedic or outpatient visit for those with documented pelvic fractures who were not hospitalized.

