**Baseline Visit:** Baseline visits will be scheduled when all results are in and within one month of fracture. Subjects will be seen in the morning after an overnight fast. Blood will be drawn and subjects will be allowed breakfast. Vitamin D supplements (1000 IU daily) will be provided to help to maintain adequate 25OHD serum levels and calcium intake will be reviewed. A blood sample will be collected at baseline and at every visit to assess calcium level for safety. Blood samples for biochemical indices of bone turnover (serum PINP for bone formation and serum CTX for bone resorption) and 25(OH)D will be obtained at baseline and every month and analyzed by batch at the Helen Hayes Hospital Regional Bone Center. Subjects will complete the lower extremity physical function tests, an Activities of Daily Living (ADLs) and SF-36 physical function survey, NRS for pain and a survey with pill count to determine narcotic use. Subjects will be randomly assigned (with separate schemes for males and females and prior BP use) to receive either TPTD 20 mcg or identically appearing placebo. Only the statistician will be aware of subject assignment and the pharmacist will distribute the appropriate TPTD or placebo medication. Subjects will be taught by the research nurse the method of daily self-administered subcutaneous injection techniques using TPTD or placebo pens, and provided written instructions for drug administration with a diary to track injections. We have extensive experience teaching subjects to administer TPTD with >90% compliance in elderly populations and subjects in the modelling recruitment phase were willing to take TPTD. Treatment will continue for the 3 months of the proposed study. Even if the fracture heals sooner, these subjects all have osteoporosis and should maintain their osteoporosis treatment for the duration of the double blind trial while other outcomes are evaluated (0 to 3 months).

**Retention:** Subjects will be called weekly during the 3 month blinded trial to monitor side effects and adverse events, and to ensure compliance with the protocol, including medication adherence.

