**Statistical Plan:** There will be no interim analysis and missing outcome data will not be imputed. Statistical analysis will be performed using SAS software (Cary NC). Between group differences at baseline will be compared with t-tests or Wilcoxon rank sum tests and chi-square tests as appropriate (p-value <0.05 for significance). Randomization by the method of randomly permuted blocks will be created for gender and BP use groups. Our primary analysis is ITT analysis and our primary outcome (SA#1) is the categorization of the level of bridging seen on focus CT into the scores from 0 to 4, described above between 0 and 3 months. The difference in cortical bridging will be evaluated by a 2x5 chi-square (group x score) with a trend test (Jonckheere-Terpstra) to see whether TPTD treated "trend" to have more higher bridging scores than the placebo group. We expect 30% - 50% superiority with TPTD at 3 months. This categorical outcome will be further analyzed with generalized estimating equations (GEE) for longitudinal repeated measures assuming a Poisson distribution with weighting from logistic regression analysis of the missingness pattern. Secondary analyses of covariates, sensitivity analyses and the "per protocol" analysis will incorporate the aforementioned approach into this aim's GEE analysis. This analysis addresses the question "Do patients treated with TPTD show more rapid fracture healing than those given placebo? For SA #2, we anticipate that the difference in pain score between the TPTD and placebo groups in the proposed study will be > 30% at each monthly time point (0-3 months). We will use a between-groups linear mixed model for repeated measures (LMMrm) to estimate the primary outcome of the difference in the mean within-subject change from baseline in the two groups at the end of the placebo controlled trial (0-3 months) and again to explore change from 3 to 12 months in the open label extension. In addition, narcotic and non-narcotic pain medication use will enter the model as time-dependent covariates. This analysis addresses the two questions, "Do patients treated with TPTD show more rapid reduction in reported pain level than those not so treated? If so, when?" For SA#3, the CSPPS is the outcome. A linear mixed model for repeated measures (LMMrm) will be used with fixed effects of treatment group (TPTD vs. placebo), time (D1, 4-, 8- and 12-wk) and their interaction, the baseline level of the CSPPS and days from injury to randomization entered as covariates, and a within-subject covariance structure selected by empirical methods prior to hypothesis testing. This plan will be repeated for the "per protocol" analysis in which subjects are limited to those showing 80% or greater compliance over the 12-week trial. This statistical plan addresses the two clinical questions, "Do patients treated with TPTD recover lower limb function faster than those not so treated? If so, when?" LMMrm will be used to analyze data from 3-12 months and assess group by time interaction. We will group on prior BP exposure strata to account for possible heterogeneity in the R-side covariance structure.

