
Imbalances in group characteristics at baseline (p-values < 0.20) will be assessed as covariates in secondary analyses and findings of significant effect modification will be followed-up with sensitivity analyses. Cumulative

exposure to treatment will be entered as time dependent random effect to incorporate compliance and non-completer data. Other outcomes will be similarly analyzed in secondary analyses. The following variables will be considered and tested as potential covariates in these models using  $p<0.2$  correlation with outcome as criterion: gender, age, baseline 25(OH)D, pre-fracture SF36 physical function score, Charlson Comorbidity scale, concomitant medications, recent BP use, fracture severity (displacement) and fracture category (single or multiple fractures or sacral and pubic).

**Sample Size Justification:** We will recruit 100 female and male subjects over 4 years (30, 30, 30, 10) to yield 80 analyzable subjects completing 3 months of treatment after assuming a 20% overall drop-out rate. Power and sample size were calculated for SA#1 fracture healing by radiographic studies: if 100% of TPTD and 60% of placebo have completed fracture healing by three months, 40 subjects per group provides  $> 95\%$  power with 1% alpha to detect this difference based on an analysis of proportions. For the Timed Up and Go Test assuming Peichel's results (at week 12 TPTD =  $22.9 \pm 7.7$  vs Placebo =  $54.3 \pm 19.9$ ), a SD of 18 and a week 4 to 12 pattern of rapid fracture healing in the TPTD group (at week 8 100% vs 9% in Placebo). A repeated measures ANOVA with a Hotelling-Lawly F-test, the same as the Wald test in the LMMrm model with unstructured covariance matrix, shows 90% power at 1% alpha is achieved for the fixed treatment effect with 33 subjects per group and time-by-treatment interaction with 36 subjects per group (SAS 9.4 GLMPOWER).

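### The SA#1 cortical-bridging analysis does not prespecify adjustment for days from injury to randomization, a fixed covariate in SA#3; adding it is a cheap improvement, not the repair of an error

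*Combined protocol and SAP*

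**What the plan says.** For SA#1, the Statistical Plan (section 7) states: "The difference in cortical bridging will be evaluated by a 2x5 chi-square (group x score) with a trend test". The Protocol Summary describes the same analysis, and neither place gives the test a covariate.

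A weighted Poisson GEE over the monthly readings follows, and the Statistical Plan ties it to the question "Do patients treated with TPTD show more rapid fracture healing than those given placebo". The Protocol Summary sets rules for imputing missing covariates directly after describing this GEE, so the model is meant to contain some. They are not named there.

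The SA#3 physical-function model is explicit: "the baseline level of the CSPPS and days from injury to randomization entered as covariates".

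The Statistical Plan gives two general routes by which a covariate can enter:
- The imbalance rule: "Imbalances in group characteristics at baseline (p-values < 0.20) will be assessed as covariates in secondary analyses".
- A candidate list screened on correlation with outcome: "gender, age, baseline 25(OH)D, pre-fracture SF36 physical function score, Charlson Comorbidity scale, concomitant medications, recent BP use, fracture severity (displacement"), followed by fracture category. Time since injury is not on it.

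Randomization and Medication (section 4) stratifies by sex and bisphosphonate use only.

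On timing, radiographs are taken "At 4, 8 and 12 weeks after initiating TPTD or TPTD placebo", and "Baseline visits will be scheduled when all results are in and within one month of fracture". The Protocol Summary expects treatment to begin within 2 weeks of fracture, and the Screening visit text gives 2 weeks as a goal. The Study Design overview, Recruitment, and Randomization and Medication all allow one month.

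**The concern.** SA#1 asks whether healing is faster, and each reading is timed from first dose rather than from fracture. A patient dosed on day 28 carries a fracture almost four weeks older at the 12-week reading than one dosed on day 2. If older fractures show more bridging, that spread adds noise to the comparison. When the arms differ in delay by chance, it also tilts the result towards the arm that started later.

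The plan treats this variable as important enough to fix in advance for SA#3, yet leaves its use in SA#1 to a data-dependent trigger that cannot reach the primary test. At stake are some precision and some protection against chance imbalance. Validity is not at stake.

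**Working it through.** **1. The plan's own figure.** Sample Size Justification: 40 per group, 100% vs 60% healed, alpha 1%, power above 95%. Normal approximation, two-sided, mean proportion 0.80:

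z = [0.40 × √40 − 2.576 × √(2 × 0.80 × 0.20)] / √(0.60 × 0.40) = (2.530 − 1.457) / 0.490 = 2.19, so power is 98.6%.

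Fisher's exact test gives 99.8%. The stated figure reproduces, and leaving out the covariate does not disturb it.

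**2. Spread of fracture age.** The documents do not give the distribution of delay, so these cases are assumptions.
- Even over 2-30 days: SD = 28/√12 = 8.08 days. Fracture age at the 12-week reading runs from 12 + 2/7 = 12.3 to 12 + 30/7 = 16.3 weeks, and 16/28 = 57% start after day 14.
- Tighter: median 9 days, lognormal (log-SD 0.6) truncated to 2-30, SD 5.57, 21% after day 14. The median is borrowed from the hospital stay under Recruitment ("during their initial hospitalization (median length of stay is 9 days"), which is not itself a treatment delay.
- Narrow: even over 2-14 days, reflecting the 2-week goal.

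**3. How prognostic fracture age might be.** The only healing slope in the documents is in the Background: controls 9% healed at 8 weeks and 68% at 12 weeks. On the logit scale, (0.754 + 2.314)/4 = 0.767 per week, or 0.110 per day. It comes from a nonrandomized study, and the documents do not say when the control clock started.

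**4. Trend-test power.** Simulation: 40 per arm, five-level proportional-odds score, two-sided 5%, treatment log odds ratio 1.3 (TPTD 81-85% healed when placebo is 60%). Placebo is set to 60% healed at 12 weeks except in the last row. Cells show unadjusted / van Elteren at 14 days / rank ANCOVA, in percent.

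| Slope per day | Even 2-30 days | Tighter, median 9 |
|---|---|---|
| 0 | 84.0 / 83.8 / 83.5 | 84.1 / 83.2 / 83.2 |
| 0.020 | 84.6 / 84.0 / 84.0 | 84.4 / 83.8 / 83.6 |
| 0.045 | 82.0 / 82.5 / 82.3 | 84.0 / 84.1 / 83.9 |
| 0.085 | 77.8 / 80.6 / 81.2 | 80.9 / 81.4 / 81.7 |
| 0.110, clock from first dose | 72.2 / 78.0 / 78.4 | 79.4 / 81.0 / 81.1 |
| 0.110, clock from fracture | 39.2 / 40.2 / 39.8 | 53.9 / 54.8 / 53.6 |

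The first four rows use 6000 runs and the last two 4000, so each figure has a simulation standard error of about 0.5 to 0.8 points. In the last row placebo healing is already 90% (even) or 85% (tighter) at 12 weeks, which leaves little to detect.

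Two further simulations of the steep first-dose case gave 73.8 to 80.2/80.9 and 73.8 to 79.6-80.9 with even delays. With tighter delays they gave 80.9 to 83.2/84.1 and 81.3 to 82.7-83.3. Under the narrow window, power goes from 82.2 to 83.3 at the full slope and from 83.2 to 82.7 at 0.045.

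Near the planned effect (TPTD 95-97% healed), power at 5% is 99.8-100% for every test, and the gain is at most 0.2 points. At 1% the largest gain is 98.6 to 99.6.

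**5. Chance imbalance.** With even delays, the SE of the difference in mean delay is 8.08 × √(2/40) = 1.81 days, so p = 0.20 falls at 1.28 × 1.81 = 2.3 days. With no treatment effect, the steep slope and the first-dose clock, take the 1 trial in 5 at or beyond that difference. False positives towards the later-starting arm are 10.0 / 4.5 / 2.8% against a nominal 2.5%. With tighter delays this is 1 trial in 15, at 13.1 / 6.2 / 4.4%. Over all null trials, the trend tests hold their size at 4.6-5.6%.

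**6. The GEE.** Poisson, independence working correlation, robust SE, visits at 4, 8 and 12 weeks, steep slope, first-dose clock. For the treatment effect averaged over visits, adding delay raises power from 81.7 to 88.9% (even) and from 85.7 to 89.0% (tighter). A repeat of the even case gave 82.4 to 89.0%. For treatment-by-time, power does not move: 43.6 to 43.6% and 44.1 to 44.1% in two runs with even delays, and 47.6 to 47.6% with tighter delays. A delay main effect shifts all of a patient's visits together and so drops out of within-patient change.

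**The case against.** The strongest case is that this is a preference with a benefit that depends on stacked assumptions: a steep slope, a clock running from first dose, wide delays and an effect smaller than planned. That stands. Remove any one of them and the trend-test gain shrinks, often to nothing.

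A second objection is that the GEE is aimed at change in healing scores, for which the added term buys no power. That also stands. Treating the GEE term as a free power gain would be wrong for that contrast.

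Third, the imbalance rule already covers much of the chance-imbalance case. Under even delays, a 2.3-day difference is its trigger. This stands in part: those trials would have the delay assessed in secondary analyses, but the primary test would remain unadjusted. The 14-day split also leaves some excess error (4.5-6.2% against 2.5%).

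Fourth, the simulations use 40 completers per arm. They do not include the planned coding of dropouts after adverse events as not healed, the carry-forward of other missing endpoints, or the GEE's missingness weights. This stands as a limit on the exact figures.

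Finally, the randomization strata are also unadjusted in the primary test, and nothing in the documents ranks delay above displacement, fracture number or age. That is fair. The argument for delay is that the plan already fixes it elsewhere and that it bears directly on a time-dependent endpoint.

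Two stronger readings are tempting, and the documents support neither. A reader might infer that unequal fracture age biases the primary test. Randomization prevents bias on average, and simulated size is about 5%. A reader might also infer that the SA#1 GEE has no covariates or bars this one. The imputation rules in the Protocol Summary show that covariates are intended; this one is simply not named.

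**Conclusion.** The point holds as an optional refinement. In SA#1, days from injury to randomization is neither a prespecified covariate, nor a stratum, nor a listed candidate. Its only route in is a data-driven rule confined to secondary analyses.

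For the trend test at 40 per arm and log odds ratio 1.3, the gain is about 6-7 points with even 2-30 day delays and the steep cited slope. With tighter delays it is about 1-2 points, though one of three runs gave 2.3-3.2. It is roughly zero, with a possible loss of under about 1 point, if fracture age is weakly prognostic or patients start within 2 weeks. There is no material gain at the planned effect. Adjustment also limits the influence of chance imbalance in delay on the primary test.

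Confidence is medium, because neither the delay distribution nor the prognostic strength of fracture age is given in the documents.

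**What to change.** Before unblinding, add to the Statistical Plan:
- **Trend test.** A covariate-adjusted SA#1 trend test, either rank ANCOVA on days from injury to randomization or a van Elteren test split at 14 days, reported with the unadjusted Jonckheere-Terpstra test. Name in advance which of the two is primary. Rank ANCOVA is the safer choice if most patients start within 2 weeks, because the split then leaves almost everyone in one stratum. Both avoid the separation that an ordinal regression model could meet if TPTD healing is near 100%.
- **GEE.** Days from injury to randomization as a fixed term in the SA#1 GEE, regardless of the p<0.20 rule. State whether the tested contrast is the averaged treatment effect or treatment-by-time. If it is the latter, consider a days-by-time term as well, since the main-effect term alone adds no power there.

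The cost is a few sentences and no new data, because SA#3 already requires the variable. The price is a possible loss of under about 1 power point in the trend test if fracture age turns out to be weakly prognostic.

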For the secondary outcome of pain, we will use a between-groups linear mixed model for repeated measures (LMMrm) to estimate the between-group difference in the mean within-subject change from baseline to the end of the placebo controlled trial (0-3 months) and again to explore change from 3 to 12 months in the open label extension. Narcotic and non-narcotic pain medication use will enter the model as time-dependent covariates. Separately, treatment group differences in the cumulative narcotic and non-narcotic drug exposure in the 3-month placebo-controlled phase will also be estimated with linear mixed model for repeated measures. This analysis addresses the two questions, “Do patients treated with TPTD show more rapid reduction in reported pain level than those not so treated? If so, when?”

For the secondary outcome of lower limb physical function, we will use a between-groups linear mixed model for repeated measures (LMMrm) model for the analysis to estimate the difference in within-subject change from 0 to 3 months in the CSPP score in the two groups. A secondary analysis for this aim will explore the changes in physical function from 3 to 12 months in the two groups.

If TPTD can improve fracture healing, this study will have an impact on the treatment of persons with pelvic fracture who are not surgical candidates and often face severe pain, chronic immobility, and loss of function in the elderly. A positive finding of accelerated healing of pelvic fractures would also encourage study of TPTD for treatment of other osteoporotic fractures.

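### As worded, the SA#2 pain model leaves its main change-from-baseline estimate unadjusted for baseline NRS and days from injury, and so gives up free precision on a secondary outcome

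*Combined protocol and SAP*

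**What the plan says.** - **Pain target.** The Statistical Plan (section 7) uses a linear mixed model for repeated measures for SA#2 to "estimate the primary outcome of the difference in the mean within-subject change from baseline in the two groups at the end" of the three-month blinded phase. The Protocol Summary has the same target: to "estimate the between-group difference in the mean within-subject change from baseline to the end of the placebo controlled trial".
- **Pain covariates.** Only medication terms are named: "In addition, narcotic and non-narcotic pain medication use will enter the model as time-dependent covariates".
- **Function model, same paragraph.** SA#3 has "the baseline level of the CSPPS and days from injury to randomization entered as covariates".
- **Availability.** Baseline NRS is collected: "The NRS and recording of pain medications will be done at baseline, 4, 8 and 12 week visits". Days from injury must be on file because SA#3 uses it.
- **Spread of entry times.** "Baseline visits will be scheduled when all results are in and within one month of fracture".
- **Randomisation.** Strata are gender and bisphosphonate use only.
- **Candidate covariates.** The list reads "gender, age, baseline 25(OH)D, pre-fracture SF36 physical function score, Charlson Comorbidity scale, concomitant medications, recent BP use", then adds fracture severity and fracture category. Neither baseline NRS nor days from injury is on it.
- **Imbalance rule.** A separate sentence sends baseline characteristics that differ at p < 0.20 into secondary analyses as possible covariates.

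**The concern.** The plan treats starting level and time since injury as worth adjusting for in function, but names neither for pain and gives no reason. Pain after an acute fracture plausibly depends on both, and day 1 can fall anywhere up to a month after the fracture.

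Two things are at stake. The first is precision: a change-score contrast generally uses the day 1 value less efficiently than a regression on it. The second is the estimate in the one trial that will be run. If the arms differ by chance in day 1 pain, regression to the mean moves part of that difference, with its sign reversed, into the estimated treatment effect. With about 40 analysable patients per arm and no stratification on pain, such imbalances will not be negligible.

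**Working it through.** **The plan's own figures.** No SD, correlation or power is given for pain. The 40 per arm used below comes from the Sample Size Justification for SA#1: 100% against 60% healed, 1% alpha, more than 95% power. With a pooled two-sided test, the null SE is √(2 × 0.8 × 0.2 / 40) = 0.0894 and the alternative SE is √(0.6 × 0.4 / 40) = 0.0775. Then (0.4 − 2.576 × 0.0894) / 0.0775 = 2.19, which is power of 98.6%. Inflating for drop-out, 80 / (1 − 0.20) = 100. Both figures reproduce.

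**Which analysis the wording implies.** SA#2 does not say how day 1 enters the model. If day 1 NRS is a response with free arm means, then with complete data and before any time-varying covariate, the arm contrast in change is the difference in raw mean changes.

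**General variance comparison.** Let s0 and s1 be the SDs at day 1 and week 12, and r their correlation. Per patient:

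- change score: s0² + s1² − 2·r·s0·s1
- baseline-adjusted (large sample): s1²(1 − r²)
- difference: (s0 − r·s1)²

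The difference is never negative. It is zero only when the slope of week 12 on day 1, r·s1/s0, equals 1.

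**Equal SDs (assumed).** The ratio of adjusted to change-score variance is (1 − r²) / [2(1 − r)] = (1 + r)/2. The SE of an arm difference is √(variance × 2/40). The NRS SD of 2.5 is also an assumption.

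| r (assumed) | Variance ratio | SE, change (SD units) | SE, adjusted (SD units) | SE in NRS points at SD 2.5 | CI narrower by 1 − √ratio | Change-score n per arm matching 40 adjusted (40/ratio) |
|---|---|---|---|---|---|---|
| 0.3 | 0.65 | 0.265 | 0.213 | 0.66 to 0.53 | 19% | 62 |
| 0.5 | 0.75 | 0.224 | 0.194 | 0.56 to 0.48 | 13% | 53 |
| 0.7 | 0.85 | 0.173 | 0.160 | 0.43 to 0.40 | 8% | 47 |

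**Carry-over of chance imbalance.** The day 1 difference between arms has SD √(2/40) = 0.224 SD units. The share passed into the change estimate, with reversed sign, is 1 − r: 70%, 50% or 30%. In a simulation of 20,000 trials per value of r at 40 per arm, the slope of the estimate on the imbalance was −0.70, −0.51 and −0.31 for change scores, and 0.00, −0.01 and 0.00 after adjustment. The simulated variance ratios were 0.66, 0.75 and 0.86.

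**Reach of the imbalance rule.** Reaching p < 0.20 at 40 per arm needs a difference of 1.282 × 0.224 = 0.29 SD (at 50 per arm, 1.282 × 0.200 = 0.26 SD). Smaller imbalances do not trigger the rule. Larger ones lead only to a secondary analysis.

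**Days from injury.** The documents give no partial correlation with pain, so no gain can be computed.

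**The case against.** The strongest reply is that silence is not exclusion. No sentence says that the pain model is unadjusted. The Protocol Summary describes SA#3 in similar within-subject-change terms and names no covariates there, yet the Statistical Plan shows that SA#3 does adjust. A reader might infer that the sponsor chose an unadjusted pain analysis. The documents do not support that; they leave the covariates unspecified. What remains is that the detailed paragraph lists these terms for one aim and not for the next, so an analyst following it would not include them.

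Three further points stand as limits:

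- Day 1 is named as a time level only for SA#3. Treating it as an unconstrained response for pain is an inference. With the 20% drop-out that the plan expects and time-varying medication terms, the match to a raw change score is not exact.
- It is tempting to say that a change score is less precise whenever the correlation is below 1. That needs equal SDs. At r = 0.7 and s1/s0 = 1.43, for example, the slope is 1 and the gain disappears. Unequal SDs can make the gain larger or smaller than in the table.
- It would also be too strong to say that nothing in the plan could bring these variables in. The p < 0.20 rule is not confined to the candidate list and could reach both, but it leaves the main estimate as it is.

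The objection that pain is secondary and unpowered bears on priority. It does not remove the point.

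**Conclusion.** The point holds as a free improvement to a secondary outcome. Followed as worded, the plan gives a main SA#2 estimate without baseline NRS or days from injury, although both are available and SA#3 uses the equivalent terms.

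Under equal SDs, r between 0.3 and 0.7 and complete data, baseline adjustment would narrow the interval by about 19% to 8%. It would also remove the 70% to 30% of a chance day 1 imbalance that a raw change contrast retains. These figures are conditional on assumptions that the documents neither give nor contradict. The days-from-injury part rests on consistency with SA#3 and on the spread of entry times alone.

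A reader might go further and call the pain estimate biased or the trial underpowered. Neither follows. Randomisation keeps a change-score contrast unbiased on average, and the difficulty is conditional on the imbalance observed. No power is claimed for pain, and the primary outcome is untouched.

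**What to change.** State the SA#2 model in full: a mixed model of NRS at weeks 4, 8 and 12 on arm, visit, arm-by-visit, day 1 NRS, day 1 NRS-by-visit, and days from injury to randomisation. Alternatively, keep day 1 as a response with the arm means constrained equal at day 1, and add days from injury.

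Say explicitly that this change leaves the plan's time-dependent pain-medication terms as they are. Use the same baseline-adjusted form for TUG, ADL and SF-36, which the plan covers only by saying that other outcomes are analysed in a similar way.

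Do not carry over the SA#3 wording. It lists D1 among the time levels and also enters baseline CSPPS as a covariate, so baseline is used twice.

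The cost is SAP wording only, and it should be settled before unblinding so that the covariates are not chosen with results in view. No new data are needed, and no stated power or sample size changes.
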